### 17.3 Reporting and Exclusions

All patients included in the study must be assessed for safety, tolerability, and response to treatment, even if there are major protocol treatment deviations or if they are ineligible. Each patient will be assigned one of the following categories: 1) complete response, 2) partial response, 3) stable disease, 4) progressive disease, 5) early death from malignant disease, 6) early death from toxicity, 7) early death because of other cause, or 9) unknown (not assessable, insufficient data). All of the patients who met the eligibility criteria (with the possible exception of those who received no study medication) should be included in the main analysis of the response rate. Patients in response categories 4-9 should be considered to have a treatment failure (disease progression). Thus, an incorrect treatment schedule or drug administration does not result in exclusion from the analysis of the response and clinical benefit rate.

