Encouraging phase II data in patients with ER+/HER2-negative postmenopausal patients with newly diagnosed MBC indicated that the addition of palbociclib to letrozole extends PFS with a tolerable safety profile. The multicenter randomized phase I/II PALOMA-1 study evaluated the combination of palbociclib with the AI letrozole vs. letrozole alone in patients with previously untreated metastatic ER+/HER2-negative MBC. The phase I component of the study established the safety of this combination. The phase II component of the study accrued 165 patients and was divided into two parts, with the first part open to all participants in the study and a second part open only to patients selected for *CCND1* amplification or p16 loss (N=99). After exploratory analysis failed to demonstrate that *CCND1* amplification or p16 loss predicted response to palbociclib, the two parts were combined for a final efficacy analysis. Compared to letrozole alone, the combination of palbociclib and letrozole provided a very impressive increase in PFS, the predefined primary outcome, from 10.2 months to 20.2 months [Hazard Ratio (HR)=0.37;  $p=0.0004$ ]. Based on these results, in February 2015 the FDA granted accelerated approval for the use of palbociclib and letrozole as first line treatment of patients with ER+/HER2-negative MBC. The confirmatory phase III randomized PALOMA-2 study completed accrual and its preliminary results have been presented at the 2016 American Society of Clinical Oncology (ASCO) meeting. A total of 666 post-menopausal patients with no prior systemic therapy for ER+ MBC were randomized 2:1 to receive letrozole with palbociclib or letrozole with placebo. Median PFS (primary endpoint) was 24.8 months vs. 14.5 months in favor of the palbociclib arm (HR=0.58 [0.46–0.72],  $p < 0.000001$ ). Response rate was also improved in the palbociclib arm (42.1% vs. 34.7%,  $p=0.031$ ; 55.3% vs. 44.4% in patients with measurable disease [ $p=0.013$ ]), and clinical benefit rate was 84.9% vs. 70.3% ( $p < 0.0001$ ).

The double blind phase III PALOMA-3 trial investigated the combination of fulvestrant and palbociclib in 521 pre- and post-menopausal patients with ER+/HER2-negative MBC, with disease relapse or progression after at least one line of hormonal therapy and at most one line of

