## 4. PARTICIPANT SELECTION

#### 4.1 Inclusion Criteria

- 4.1.1 Patients (female or male) must provide informed written consent and must complete all screening assessments as outlined in the protocol
- 4.1.2 Patients must be able to swallow and retain oral medication
- 4.1.3 Patients must be  $\geq 18$  years of age
- 4.1.4 Female patients of no childbearing potential.

Patient must be post-menopausal by at least one of the following criteria prior to enrollment:

- a. Subjects at least 60 years of age; OR
- b. Subjects under 60 years of age and naturally (spontaneous, no alternative pathologic or physiological cause) amenorrhea for at least 12 months; OR
- c. Medical ovarian failure confirmed by follicle-stimulating hormone (FSH) and estradiol levels in the post menopausal range per local institutional normal range; OR
- d. Prior bilateral oophorectomy; OR
- e. Prior radiation castration with amenorrhea for at least 6 months; OR
- f. Treatment with a luteinizing hormone-releasing hormone (LH-RH) agonist (such as goserelin acetate or leuprolide acetate) is permitted for induction of ovarian suppression as long as it has been initiated at least 28 days prior to study enrollment

- 4.1.5 ECOG performance status 0 - 1

- 4.1.6 Clinical stage IV or inoperable locoregional recurrent invasive mammary carcinoma that is:

- a. ER+ and/or PgR+ ( $\geq 1\%$  positive stained cells) by immunohistochemistry (IHC)
- b. HER2-negative (by IHC or FISH, per ASCO guidelines)
- c. *FGFR1 – 4 amplified\** (may be determined by local assessment through either targeted capture next generation sequencing (NGS), plasma cell-free tumor [cf] DNA or FISH [in the case of *FGFR1* amplifications]\*) in 50% of the patients participating in the expansion cohort of the trial (not necessary in the escalation cohort)

*\*Cases will be considered as *FGFR1*-positive ('amplified') under one of the following conditions:*

- (1) The *FGFR1/CEN8* ratio is  $\geq 2.0$ ;*
- (2) The average number of *FGFR1* signals per tumor cell nucleus is  $\geq 6^{40}$*

- d. Evaluable (may have either measurable or non-measurable disease)

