### 12.1 Definitions

Evaluable for toxicity: All patients will be evaluable for toxicity from the time of their first administration of study treatment drugs.

Evaluable for objective response: Only those patients who have measurable disease present at baseline, have received at least one cycle of therapy, and have had their disease re-evaluated will be considered evaluable for response. These patients will have their response classified according to the definitions stated below.

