##### 12.2.3.1 Bone lesions:

- Bone scan, PET scan or plain films are not considered adequate imaging techniques to measure bone lesions. However, these techniques can be used to confirm the presence or disappearance of bone lesions
- Lytic bone lesions or mixed lytic-blastic lesions, with identifiable soft tissue components, that can be evaluated by cross-sectional imaging techniques such as CT or MRI can be considered as measurable lesions if the soft tissue component meets the definition of measurability described above
- Blastic bone lesions are non-measurable

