### 12.3.2 Evaluation of Target Lesions

12.3.2.1 Complete Response (CR): Disappearance of all target lesions. Any pathological lymph nodes (whether target or non-target) must have reduction in short axis to <10 mm.

12.3.2.2 Partial Response (PR): At least a 30% decrease in the sum of diameters of target lesions, taking as reference the baseline sum diameters.

12.3.2.3 Progressive Disease (PD): At least a 20% increase in the sum of diameters of target lesions, taking as reference the smallest sum on study (this includes the baseline sum if that is the smallest on study). In addition to the relative increase of 20%, the sum must also demonstrate an absolute increase of at least 5 mm. (Note: the appearance of one or more new lesions is also considered progression).

12.3.2.4 Stable Disease (SD): Neither sufficient shrinkage to qualify for PR nor sufficient increase

to qualify for PD, taking as reference the smallest sum of diameters while on study.

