#### 12.3.4 Evaluation of Non-Target Lesions

12.3.4.1 Complete Response (CR): Disappearance of all non-target lesions and normalization of tumor marker levels. All lymph nodes must be non-pathological in size (<10 mm in their short axis).

12.3.4.2 Non-CR/Non-PD: Persistence of one or more non-target lesion(s) and/or maintenance of tumor marker levels above the normal limits.

12.3.4.3 Progressive Disease (PD): Unequivocal progression of existing non-target lesions. (Note: the appearance of one or more new lesions is also considered progression).

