#### 12.3.5 Evaluation of Best Overall Response

The best overall response is the best response recorded from the start of the study treatment until the end of treatment taking into account any requirement for confirmation. On occasion a response may not be documented until after the end of therapy so protocols should be clear if post-treatment assessments are to be considered in determination of best overall response. Protocol must specify how any new therapy introduced before progression will affect best response designation. The patient's best overall response assignment will depend on the findings of both target and non-target disease and will also take into consideration the appearance of new lesions. Furthermore, depending on the nature of the study and the protocol requirements, it may also require confirmatory measurement. Specifically, in non-randomized trials where response is the primary endpoint, confirmation of PR or CR is needed to deem either one as the 'best overall response'.

Target Lesions	Non-Target Lesions	New Lesions	Overall Response
CR	CR	No	CR
CR	Non CR/Non PD	No	PR
CR	Not evaluated	No	PR
PR	Non PD or not all evaluated	No	PR
SD	Non PD or not all evaluated	No	SD
Not all evaluated	Non PD	No	NE
PD	Any	Yes or no	PD
Any	PD	Yes or no	PD
Any	Any	Yes	PD

CR=complete response, PR=partial response, PD=progressive disease, SD=stable disease, NE=not evaluable.

\* In exceptional circumstances, unequivocal progression in non-target lesions may be accepted as disease progression.

Note: Patients with a global deterioration of health status requiring discontinuation of treatment without objective evidence of disease progression at that time should be reported as "*symptomatic deterioration*". In these patients, every effort should be made to document the objective progression even after discontinuation of treatment.

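### The plan does not classify a progression-free patient who has only non-measurable disease, and its sections give opposite answers for the clinical benefit rate

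*Combined protocol and SAP*

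**What the plan says.** **Eligibility.** Section 4.1.6d asks only for disease that is "Evaluable (may have either measurable or non-measurable disease". Section 12.2.3.1 gives a common example of the second kind: "Blastic bone lesions are non-measurable".

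**Evaluability.** Section 12.1 limits the patients whose response can be classified as follows: "Only those patients who have measurable disease present at baseline, have received at least one cycle of therapy, and have had their disease re-evaluated".

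**Lesion-level definitions.** Stable disease appears only in 12.3.2, for target lesions, and rests on the sum of their diameters: "Neither sufficient shrinkage to qualify for PR nor sufficient increase" for PD. Non-target disease that is neither gone nor progressing is Non-CR/Non-PD in 12.3.4.2: "Persistence of one or more non-target lesion(s) and/or maintenance of tumor marker levels above the normal limits".

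**Overall response.** Section 12.3.5 states: "The patient's best overall response assignment will depend on the findings of both target and non-target disease". Every row of its table that does not give PD starts from a target-lesion result.

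**Analysis categories.** Section 17.3 assigns each patient one category: CR, PR, stable disease, progressive disease, three kinds of early death, or unknown. It puts the eligible patients (with a possible exception for those never dosed) into the main response-rate analysis and then says: "Patients in response categories 4-9 should be considered to have a treatment failure (disease progression". Its closing sentence names the clinical benefit rate.

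**CBR.** Section 2 counts CR, PR, and stable disease without progression at 6 months. Section 7.1 describes CBR as absence of progression for at least 6 months and names no response category. Section 17.2.2 reports CBR as a percentage with a 95% CI and sets no target or test.

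**The concern.** A patient with blastic bone disease only can enrol, be scanned every 8 weeks and remain progression-free well past 6 months. Nothing in 12.3.5 or 17.3 says what this patient's overall response is. The sections that bear on it pull apart: 12.1 with 17.3 leads toward treatment failure, and 7.1 leads to clinical benefit.

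If the first reading is applied, CBR is understated by an amount that depends on the case mix, and a patient who is event-free at 6 months on the Kaplan–Meier PFS curve is labelled as progression in the CBR table. If the choice is left to sites, some will record stable disease and others not evaluable, so CBR will partly reflect coding habit. The trial is small: one recoded patient moves CBR by 1/35 = 2.9 points at the planned maximum and 1/26 = 3.8 points at the minimum.

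**Working it through.** The plan states no CBR figure, target or power, so there is nothing to reproduce. The check is a trace through the text, then a sensitivity calculation.

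**Trace of a patient with no target lesions and controlled non-target disease**

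1. Enrols under 4.1.6d.
2. At lesion level is Non-CR/Non-PD (12.3.4.2). Stable disease under 12.3.2.4 cannot be derived, because there is no sum of diameters.
3. In the 12.3.5 table, the rows giving CR, PR or SD need a target-lesion CR, PR or SD. The NE row is for target lesions not all evaluated, which presupposes that some exist. Only the PD rows that accept any target status could apply, and this patient has not progressed. The table is silent. It is also silent for a patient whose non-target lesions all disappear, so ORR has the same gap.
4. Section 12.1 makes the patient not evaluable for objective response.
5. Section 17.3 requires a category. If not evaluable is carried over, the only fitting entry is unknown (category 9), which lies in the failure group.
6. Section 2 counts CR, PR and SD only, so the patient is not a CBR success. Under 7.1 the same patient is.

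**Size of the disagreement**

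Let m be the share with non-measurable disease only, b the share of those progression-free at 6 months, and c the clinical benefit share among patients with measurable disease. All patients stay in the denominator.

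- Counted as benefit: CBR = (1 − m)c + mb
- Counted as failure: CBR = (1 − m)c
- Difference = mb, whatever c is

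The documents give neither m nor b. Over assumed ranges of m = 10–40% and b = 40–70%:

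- lowest: 0.10 × 0.40 = 0.04, or 4 points
- highest: 0.40 × 0.70 = 0.28, or 28 points

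**Two illustrations at the planned sample sizes (26 and 35, synopsis).** The number with non-measurable disease only and the benefit of about 60% are assumptions. Intervals are Wilson 95%; 17.2.2 does not name an interval method.

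| N | Non-measurable only (progression-free) | Counted as benefit | Counted as failure | Measurable disease only |
|---|---|---|---|---|
| 35 | 10 (6) | 21/35 = 60% (44–74%) | 15/35 = 43% (28–59%) | 15/25 = 60% |
| 26 | 5 (3) | 16/26 = 62% (43–78%) | 13/26 = 50% (32–68%) | 13/21 = 62% |

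Check against the formula: (10/35)(6/10) = 6/35 = 17.1 points, and (5/26)(3/5) = 3/26 = 11.5 points. Both match the table.

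**The case against.** The strongest reply is that the plan never says these patients are failures. A reader might infer that 17.3 makes scoring them as progression the rule. The documents do not support that: no sentence codes a non-progressing patient without target lesions as unknown, category 3 in 17.3 is not limited to measurable disease, and years of regular scans are hardly insufficient data. The failure sentence in 17.3 also follows a statement about the response rate; CBR is named only in the sentence after it, which concerns dosing errors. Section 7.1 would credit the patient. And if the population in 12.1 governed CBR, these patients would leave the denominator: in the illustrations the rate would then be 15/25 or 13/21, with no loss.

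All of this stands against a claim of established bias. None of it closes the gap. It shows three available treatments of the same patient (success, failure, excluded), each with textual support.

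A reader might also size the effect from the first-line palbociclib trial described in 3.2.1, which reports response of 42.1% vs. 34.7% overall and "55.3% vs. 44.4% in patients with measurable disease". Dividing gives 0.421/0.553 = 0.761 and 0.347/0.444 = 0.782, hence 22–24% non-measurable. That needs responses to be confined to measurable disease and the same case mix here. Those patients had no prior systemic therapy for metastatic disease, whereas 4.1.8 requires at least one prior line. The documents do not support carrying the share over, so it is not used.

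Finally, CBR drives no decision. That is correct and limits the importance of the point.

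**Conclusion.** The point holds as an internal inconsistency in a named secondary endpoint. The plan enrols patients for whom it defines no non-progression overall response, and its sections then score the same progression-free patient as a failure (12.1 with 17.3 and Section 2) or as a benefit (7.1, in line with PFS). The failure reading is a literal inference from those sections, not a stated rule.

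On that reading CBR is biased downward by m × b. The 4 to 28 points rest on assumed ranges for both quantities and on keeping all patients in the denominator. The actual size cannot be computed, because the documents do not give the share with non-measurable disease only. DLT assessment, MTD, the 8-week tolerability rule and the Kaplan–Meier PFS analysis are not affected. It should be corrected before response data are summarised, but it does not threaten the trial's primary conclusions.

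**What to change.** - **12.3.5:** add a response table for patients with non-target disease only, with outcomes CR, Non-CR/Non-PD, NE and PD.
- **17.3:** add Non-CR/Non-PD as a category that is not treatment failure. The list currently skips number 8, so the numbering can be repaired at the same time.
- **Sections 2, 7.1 and 17.2.2:** use one CBR definition, under which Non-CR/Non-PD without progression at 6 months counts as clinical benefit.
- **7.9, 12.1 and 17.3:** reconcile the response populations, which are at present, respectively, at least 8 weeks of treatment; measurable disease with at least one cycle and a re-evaluation; and the eligible patients.
- **Reporting:** give ORR and CBR also separately for measurable and non-measurable-only disease.

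The cost is wording, one added code on the response eCRF and one small extra display. No scans, visits or patients are added. The downside is that Non-CR/Non-PD is a softer judgement than stable disease measured on diameters; the separate display makes visible how much of CBR rests on it.

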## 19. MEDICATIONS TO BE USED WITH CAUTION

Please note this is not an exhaustive list. Alternatives to concurrent administration of erdafitinib and the below medications should be sought; if no alternative treatment is available, the Study Chair should be consulted.

### Moderate and Strong CYP3A4 Inhibitors: Moderate and Strong CYP3A4 Inducers:

Aprepitant	Bosentan
Atazanavir	Carbamazepine
Boceprevir	Efavirenz
Clarithromycin	Enzalutamide
Cobicastat	Fosphenytoin
Conivaptan	Lumacaftor
Diltiazem	Mitotane
Erythromycin	Modafanil
Fluconazole	Nafcillin
Fosamprenavir	Phenytoin
Grapefruit Juice	Phenobarbital
Idelalisib	Primidone
Imatinib	Rifampin
Indinavir	Rifapentine
Itraconazole	St. John's Wort
Ketoconazole	
Lopinavir	
Nefazodone	
Nelfinavir	
Nilotinib	
Posaconazole	
Ritonavir	
Saquinavir	
Suboxone	
Telaprevir	
Telithromycin	
Verapamil	
Voriconazole	

### Moderate and Strong CYP2C9 Inhibitors:

Amiodarone  
Delavirdine  
Efavirenz  
Fluconazole  
Fluvastatin  
Miconazole

### Moderate and Strong CYP2C9 Inducers:

Enzalutamide  
Phenobarbital  
Primidone  
Rifapentine

### Moderate and Strong P-gp Inhibitors:

Amiodarone  
Clarithromycin  
Erythromycin

### Moderate and Strong P-gp Inducers:

Carbamazepine  
Rifampin  
St. John's wort

Ketoconazole  
Quinidine  
Saquevir  
Verapamil

Tipranavir
